6.2.1.2. North Star Ambulatory Assessment - Total Scores

The NSAA consists of 17 activities, each scored as 0, 1, or 2. The sum of 16 scores (except for lifts head) will be used to form a total score [Mayhew 2013a]. Hereafter, this NSAA total score will be referred to as revised NSAA (rNSAA) total score. If an activity cannot be performed due to disease progression/LoA, a score of 0 will be assigned, and will not be considered as missing. If fewer than 13 of the 16 activities are performed, the total score will be considered missing. If from 13 to 16 activities are performed, the total score will be standardized by multiplying the sum of the scores in the x activities by 16/x.

The change from baseline in rNSAA total score at Week 72 based on the mITT population will be the second key secondary endpoint. An ANCOVA model will be used to evaluate the difference in change in rNSAA from baseline to Week 72 after missing data have been imputed via a pattern mixture model utilizing MI. The ANCOVA model will include factors of baseline

concomitant corticosteroid type (deflazacort, prednisone/prednisolone), baseline 6WMD category (<300 meters, 300 to <350 meters, 350 to <400 meters, \geq 400 meters), and treatment, and covariate of baseline rNSAA total score. The estimated difference in the change at Week 72 will be provided.

If both primary efficacy endpoint and the first key secondary endpoint are statistically significant at the 0.05 significance level, the rNSAA will be tested at the 0.05 (two-sided) significance level.

The same ANCOVA model will also be performed on linear transformation of the total score [Mayhew 2013a].

As a sensitivity analysis, rNSAA total score and linear score will be analyzed using a MMRM model with a random intercept. The MMRM model will include baseline concomitant corticosteroid type (deflazacort, prednisone/prednisolone), baseline 6WMD category (<300 meters, 300 to <350 meters, 350 to <400 meters, \geq 400 meters), treatment, visit (analysis visit as a categorical variable), the baseline rNSAA score as the covariate, as well as interaction of visit and treatment, and the interaction of visit and baseline rNSAA total score. The unstructured covariance matrix (UN) will be used in the MMRM model. Other types of covariance matrix (heterogenous Toeplitz, Toeplitz, and compound symmetric) will be explored in the case of non-convergence of UN.

A sample code is listed as below:

```
PROC MIXED data=<dataset> method=reml;  
  CLASS Cortico Subjid Trt C6WMD AVISIT;  
  MODEL N6WMD = Cortico C6WMD Trt B6WMD AVISIT AVISIT*B6WMD  
    AVISIT*TRT/CL;  
  RANDOM Int / subject=Subjid;  
  REPEATED AVISIT / type=un subject=Subjid;  
  LSMEANS TRT*AVISIT / pdiff CL;  
RUN;
```

where

N6WMD = 6WMD at each visit (Baseline to Week 72)
B6WMD = Baseline 6WMD
C6WMD = Baseline 6WMD category
Cortico = Baseline concomitant corticosteroid type
AVISIT = Analysis visits as categorical variable
Trt = Treatment group
Subjid = Subject
Int = Intercept

The same analysis will be repeated for the change from baseline in rNSAA total scores:

- ANCOVA after MI for ITT population (with additional factor of the baseline time to stand from supine (<5 seconds, \geq 5 seconds) in the model)
- MMRM model based on ITT population with additional factor of the baseline time to stand from supine (<5 seconds, \geq 5 seconds) in the model

The change from baseline in rNSAA total scores and linear scores will be summarized by visit for mITT and ITT populations, and for subgroups below for mITT and ITT populations:

- Region (North and Latin America, Europe, Asia Pacific)
- Stop codon (UAA, UAG, UGA)

In addition, the change from baseline in revised NSAA total scores and linear scores will also be summarized at each post-baseline visit for ITT population for the following subgroups:

- Baseline disease severity:
 - Baseline 6MWD <300 meters
 - Baseline 6MWD \geq 300 meters, time to rise from supine \geq 5 seconds at baseline, and 7 to 16 years old
 - Baseline 6MWD \geq 300 meters and time to rise from supine <5 seconds at baseline, or baseline 6MWD \geq 300 meters, time to rise from supine \geq 5 seconds at baseline, and younger than 7 or older than 16 years old

6.2.2. Other Secondary Efficacy Variables

6.2.2.1. Time to 10% Persistent Worsening in 6MWD

Time to 10% persistent worsening in 6MWD, defined as last time that 6MWD was not 10% worse than baseline, will be evaluated using a Log-rank test and Kaplan-Meier plot, as well as a Cox proportional hazards model (assuming similar covariates as the primary efficacy model) in both mITT and ITT populations. For subjects who do not have 10% 6MWD worsening, time to 10% persistent 6MWD worsening will be censored at the time of the last 6MWT during the double-blind period. For subjects who have all post-baseline assessments more than 10% worse than the baseline, the event will be assigned to Day 1. Subjects who become non-ambulatory will be considered to have 10% worsening at the time of becoming non-ambulatory. The proportion of 10% persistent worsening by Week 72 will also be summarized.

6.2.2.2. Timed Function Tests - Individual Test

The 3 timed function tests (10-meter run/walk, 4-stair stair-climb, and 4-stair descend) will be summarized and analyzed separately for each function test using the MMRM model assuming MAR based on both mITT and ITT populations. The MMRM model will include baseline concomitant corticosteroid type (deflazacort, prednisone/prednisolone), baseline 6WMD category (<300 meters, 300 to <350 meters, 350 to <400 meters, \geq 400 meters), respective baseline timed function test result, treatment, visit, the interaction of visit and treatment, and the interaction of week and corresponding timed function test result at baseline. The baseline time to stand from supine (<5 seconds, \geq 5 seconds) will be included in the testing model in the ITT analysis.

In addition, ANCOVA analysis after MI will be performed for the three timed function tests as sensitivity analysis. The individual TFT results will be summarized by visit during the double-blind period for mITT and ITT populations.

A separate analysis will be performed to evaluate the 10-meter run/walk results in subjects with a baseline 6WMD <300 meters in ITT population.

6.2.2.3. North Star Ambulatory Assessment – Individual Items

The frequency of loss of function of each NSAA items (score of 1 or 2 at baseline transitioning to a 0 score post-baseline) will be tabulated by treatment group for both mITT and ITT populations.

6.2.2.4. Loss of Ambulation (LoA) and Stair Climb/Stair Descend

LoA will be defined as persistent inability to perform the 10-meter run/walk test within 30 seconds at any post-baseline visit and for all remaining visits. Loss of stair-climbing will be defined as persistent inability to perform the 4-stair climb test within 30 seconds at any post-baseline visit and for all remaining visits. Loss of stair-descending will be defined as persistent inability to perform the 4-stair descend test within 30 seconds at any post-baseline visit and for all remaining visits. (Note: All subjects will have the ability to perform these tests within 30 seconds at screening and baseline, per the inclusion criteria.)

Time to LoA will be evaluated using Kaplan-Meier estimation, Log-rank test, and Cox proportional hazards model (assuming similar covariates as the primary efficacy model) in both mITT and ITT populations. Similar analyses will be performed for time to loss of stair-climbing and time to loss of stair-descending.

A separate analysis will evaluate time to LoA in subjects with baseline 6MWD <300 meters in ITT population.

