11.2.4 Baseline 6MWD

This study will enroll subjects with 6MWD ≥ 150 meters at pretreatment assessments. However, the primary analysis will be conducted in a subset of patients who have with 6MWD ≥ 300 meters at pretreatment assessments and meet additional criteria, as defined in Section 9.2.2.

The requirements that subjects enrolled in the study be able to walk ≥ 150 meters during the screening 6MWT provides an objective means to ensure that subjects are truly ambulatory, as ataluren is indicated for ambulatory patients with nmDMD. Assessing this distance is convenient because it constitutes 6 laps of a 25-meter course.

Patients with baseline 6MWD < 300 meters have a high muscle fat fraction and therefore a high risk of near-term loss of ambulation [Sweeney 2014]. To limit the variability of study results, these patients will not be included in the primary analysis population.

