6.2.4. Loss of Ambulation and Stair Climb/Stair Descend

Time to loss of ambulation (LoA), defined as persistent inability to perform the 10-meter run/walk test within 30 seconds at any post-baseline visit and for all remaining visits, will be evaluated using Kaplan-Meier estimation, Log-rank test, and Cox proportional hazards model (assuming similar covariates as the primary efficacy model) during overall treatment period based on ITT population. Similar analyses will be performed for time to loss of 4-stairs climb and time to loss of 4-stairs descend, defined as persistent inability to perform the 4-stairs climb test or 4-stairs descend, respectively, within 30 seconds at any post-baseline visit and for all remaining visits.

A separate analysis will evaluate time to LoA during the overall treatment period in subjects with study baseline 6MWD <300 meters.

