2.5. Randomization

Randomization is an accepted means to reduce bias and allows for the highest standard of evidence in documenting a treatment effect. The stratified, block randomization approach will be used. The system will assign the next available randomization number, within the list for the stratum, to the patient. Such a method allows treatment arms to be balanced with respect to the predefined stratification factors as well as for the number of subjects in each arm. The process will be established and performed centrally through an interactive response technology (IRT) system to maximize the integrity and security of the randomization and ensure appropriate access and convenience-of-use by the investigational sites.

In order to balance treatment allocation, the following stratification factors will be used:

- Baseline concomitant corticosteroid type (deflazacort, prednisone/prednisolone)
- Baseline 6MWD (<300 meters, 300 to <350 meters, 350 to <400 meters, ≥ 400 meters) where baseline 6MWD is the maximum of the Day 1 and Day 2 6MWDs
- Baseline time to stand from supine (<5 seconds, ≥ 5 seconds)

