In this study, brothers participating in the study will receive the same treatment group designation to minimize potential compromise of the study drug blinding and to reduce the chance of dosing errors within families. In the primary analysis, siblings will be considered as independent subjects. However, the assessments from two or more brothers may be highly correlated. To assess the impact of potential correlation among siblings, the primary MMRM analysis will be repeated by including only data from the first sibling for mITT and ITT populations. The baseline time to stand from supine (<5 seconds, ≥ 5 seconds) will be included in the testing model in the ITT analysis.

6.1.3.8. *Non-parametric analysis*

As a sensitivity analysis, the change from baseline at Week 72 in 6MWD using observed data between two treatment groups will be compared using Wilcoxon rank sum test stratified by baseline concomitant corticosteroid type (deflazacort, prednisone/prednisolone) and baseline 6MWD category (<300 meters, 300 to <350 meters, 350 to <400 meters, \geq 400 meters) for mITT population.

6.1.3.9. *Subgroup Analysis*

The change from baseline in 6MWD will be summarized by visit for subgroups below for mITT and ITT populations:

- Region (North and Latin America, Europe, Asia Pacific)
- Stop codon (UAA, UAG, UGA)

In addition, the change from baseline in 6MWD will be summarized at each post-baseline visit for the following subgroups based on baseline disease severity for ITT population:

- Baseline disease severity
 - Baseline 6MWD <300 meters
 - Baseline 6MWD \geq 300 meters, time to rise from supine \geq 5 seconds at baseline, and 7 to 16 years old
 - Baseline 6MWD \geq 300 meters and time to rise from supine <5 seconds at baseline, or baseline 6MWD \geq 300 meters, time to rise from supine \geq 5 seconds at baseline, and younger than 7 or older than 16 years old

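### The log-rank tests for loss of ambulation, stair climb, stair descend and 10% worsening name no strata although randomisation was stratified on predictors of these events, so in ITT they are conservative and lose power that the planned Cox model largely recovers

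*SAP*

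**What the plan says.** Double-blind SAP 6.2.2.4 covers loss of ambulation and extends the same analyses to stair climbing and stair descending, in mITT and ITT: "Time to LoA will be evaluated using Kaplan-Meier estimation, Log-rank test, and Cox proportional hazards model (assuming similar covariates as the primary efficacy model". For 10% persistent worsening in 6MWD, double-blind SAP 6.2.2.1 says the endpoint "will be evaluated using a Log-rank test and Kaplan-Meier plot, as well as a Cox proportional hazards model". Open-label SAP 6.2.4 and 6.2.1.2 repeat both specifications for the overall period in ITT. The 30-metre drop in 6.2.1.2 is to be handled in a similar way, so it inherits the same test. None of these sections names strata for the log-rank test.

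On the design, double-blind SAP 2.5 says: "The stratified, block randomization approach will be used". The factors are corticosteroid type (2 levels), baseline 6MWD (4 levels) and time to stand (2 levels). Protocol 11.2.4 says of the lowest 6MWD category: "Patients with baseline 6MWD < 300 meters have a high muscle fat fraction and therefore a high risk of near-term loss of ambulation". Protocol 11.3.2 says that a slow time to stand raises the risk of losing ambulation.

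Strata are written out elsewhere. Double-blind SAP 6.1.3.8 specifies a "Wilcoxon rank sum test stratified by baseline concomitant corticosteroid type" and by 6MWD category. The later changes document (3.1.2.6) adds time to stand to that test for ITT, and its 3.2.2.1 and 3.2.2.4 leave the time-to-event analyses unchanged.

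**The concern.** When allocation is balanced within prognostic strata, the two arms resemble each other more closely than under simple randomisation. A log-rank test that ignores the strata computes its null variance as if that balance were absent. The variance is too large and the test rejects too rarely. Pooling strata with very different hazards also dilutes the hazard ratio within strata.

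Time to loss of ambulation, stair climbing and stair descending are listed secondary endpoints at Weeks 72 and 144. The exposure is greatest in ITT, which mixes boys below 300 m with boys at or above 400 m. ITT is the set the sponsor moved to in the changes document, and the only efficacy set in the open-label SAP. The log-rank and Cox p-values can also differ simply because one uses the design factors and the other does not, and no section says which one leads.

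**Working it through.** **The plan's own figure.** No event count, hazard ratio or power is given for any time-to-event endpoint. Double-blind SAP 2.4 powers only the 6MWD slope: n per arm = 2 × (1.960 + 1.036)² × 2.058² / 1.0² = 76.05, so 77 per arm and 154 in total. This reproduces, but does not bear on these tests.

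**Inputs.** From the documents: ITT N = 359 (changes document 3.1.1), mITT planned N = 162, two-sided 5% level, 12-week visits to Week 72 and then Weeks 96, 120 and 144, and placebo subjects moving to ataluren after Week 72 (Protocol 5.2.1; open-label SAP 2.3). Assumed, because the documents are silent: 6MWD category shares of 25/20/25/30%; 72-week placebo risks of 60/25/12/3% (steep) or 35/20/12/6% (weaker); hazard ratio (HR) 0.6.

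**Hand check of the conservatism at 72 weeks, no treatment effect, event treated as yes/no.** The unstratified test uses variance p̄(1 − p̄). The real variance under balance within strata is Σ wₖpₖ(1 − pₖ).

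- Steep: p̄ = 0.150 + 0.050 + 0.030 + 0.009 = 0.239, so p̄(1 − p̄) = 0.1819. Within strata: 0.0600 + 0.0375 + 0.0264 + 0.0087 = 0.1326. Ratio 0.729, so Z has SD √0.729 = 0.854. The effective cut-off is 1.96/0.854 = 2.295, and the rejection rate is 2.2%.
- Weaker: p̄ = 0.1755, p̄(1 − p̄) = 0.1447, within strata 0.1322. Ratio 0.914, SD 0.956, cut-off 2.05, rejection rate 4.0%.

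**Simulation under the same assumptions** (exponential hazards, 1:1 within 6MWD strata, events read at visits). Ranges cover repeated runs; at 1,000 trials the Monte Carlo standard error is up to about 1.6 points.

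| ITT setting | Unstratified | Stratified by 6MWD |
|---|---|---|
| 72 weeks, steep, no effect | 2–2.5% | about 5% |
| 72 weeks, steep, HR 0.6 | 47% | 59% |
| 72 weeks, weaker, HR 0.6 | 39–42% | 42–46% |
| 144 weeks with switch, steep, HR 0.6 | 19–22% | 43–44% |
| 144 weeks with switch, weaker, HR 0.6 | 24% | 28–29% |

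In the 144-week rows both arms have the treated hazard after Week 72. In the 72-week steep setting, a Cox model adjusted for 6MWD category alone had 60% power, and rejected 5.0% of the time with no effect.

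**Second set of assumptions** (10,000 trials each, standard error up to 0.5 points): ITT 6MWD shares 20/15/20/45%, blocks of four within all randomisation cells, 5% dropout, 72 weeks, HR 0.6 for power, and time to stand and corticosteroid type also prognostic. Entries are unstratified → stratified by randomisation cell.

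| Setting (placebo risks by 6MWD category, lowest first) | Type I error | Power |
|---|---|---|
| ITT loss of ambulation, weak (15/8/5/2%) | 4.6 → 5.1% | 14.7 → 15.5% |
| ITT loss of ambulation, moderate (40/12/5/1%) | 2.8 → 5.1% | 20.4 → 26.1% |
| ITT loss of ambulation, strong (65/15/4/0.5%) | 1.0 → 4.8% | 20.1 → 36.0% |
| ITT 10% worsening, moderate (80/60/45/25%) | 2.5 → 5.2% | 64.5 → 75.0% |
| ITT 10% worsening, strong (95/75/50/20%) | 0.8 → 4.9% | 51.4 → 79.1% |
| mITT loss of ambulation (12/5/1%; 6–7 events) | 4.0 → 4.4% | 7.8 → 8.0% |
| mITT 10% worsening, moderate (65/50/30%) | 4.3 → 5.2% | 43.3 → 46.5% |
| mITT 10% worsening, strong (85/55/25%) | 2.6 → 5.2% | 38.8 → 49.7% |

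Stratifying by 6MWD category alone keeps nearly all of the gain: 35.8% against 36.0% for ITT loss of ambulation (strong), and 77.2% against 79.1% for ITT 10% worsening (strong).

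**The case against.** The strongest reply is that the plan already contains the remedy. Every log-rank test is paired with a Cox model using covariates similar to those of the primary model: corticosteroid type, 6MWD category and continuous 6MWD, with time to stand added for ITT. In the simulation a simpler Cox model matched the stratified log-rank. A reader might infer that a real delay in these milestones would be missed by the plan as a whole; the documents do not support that. What remains is that the covariates are described only as similar, and that no section names the leading test.

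Three other readings go too far. Carrying a constant hazard ratio of 0.6 to Week 144 would give 55% against 77%, but placebo subjects switch to ataluren at Week 72, so those figures do not describe this trial. A reader might also fear false positives, but the error runs the other way. Nor is the formal conclusion of the study touched: the fixed sequence (double-blind SAP 4.6) covers only the 6MWD slope, the timed function composite and NSAA. Time to 10% worsening is in neither SAP's endpoint list, and open-label SAP 9 calls it a sensitivity analysis.

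It is fair to say that the absence of strata is inferred from silence. The contrast with the explicitly stratified Wilcoxon test makes that the natural reading, not a certain one. It is also fair that the size rests on risks the documents do not give.

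**Conclusion.** The point holds as a loss of efficiency in the log-rank tests, mainly in ITT. At HR 0.6 over 72 weeks the loss is about 3 to 12 points under the first set of assumed risks. The second set moves it from under 1 point (weak gradient) to about 16 points for loss of ambulation and 28 for 10% worsening. To Week 144, with the switch, it is about 4 to 5 points with the weaker gradient and 21 to 25 with the steep one. In mITT, where time to stand is fixed at 5 seconds or more and the category below 300 m is empty, it is generally small and negligible for loss of ambulation. The exception is 10% worsening under a strong gradient (about 11 points).

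The direction rests on the stratified design and the protocol's own account of the predictors; the size rests on the assumed shares, risks and hazard ratio. Since the adjusted Cox model recovers most of the loss, this is a worthwhile improvement in specification and not a threat to the trial's inference.

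**What to change.** Open-label SAP 6.2.1.2 and 6.2.4, before the final lock: specify a log-rank test stratified by baseline 6MWD category and time to stand in ITT, with the merging rule in Section 4.10. Name in advance either this test or the adjusted Cox model as the main comparison, and list the Cox covariates. Naming a main test is needed even after stratifying, because the two need not agree: the Cox model may also carry continuous 6MWD.

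Week 72 (double-blind SAP 6.2.2.1 and 6.2.2.4): the data were locked in April 2022 and treatment differences have been reported, so the planned test should stand. Report beside it, labelled post hoc, a log-rank test stratified by 6MWD category and time to stand in ITT and by 6MWD category in mITT, with the merging rule in Section 4.9.

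Do not add corticosteroid type as a stratum where cell sizes allow. That choice would depend on the data, and 6MWD category already brings nearly all of the gain.

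Cost: a phrase in each section, slightly more analysis work, no new data, and a second Week 72 p-value to explain.

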6.3. Exploratory Variables

6.3.1. PUL and DMD Upper Limb PROM

PUL includes 22 items (with an entry item to define starting functional level), and 21 items subdivided into shoulder level (4 items), elbow level (9 items), and distal level (8 items) dimensions. The DMD Upper Limb PROM includes 32 items categorized in 4 domains of daily life: food (7 items), self-care (8 items), household and environment (6 items), and leisure and communication (11 items). The domain subscores will be calculated by summing the scores from all items within each domain, and the total score will be calculated as the sum of all domain scores. A domain subscore is considered missing if any of the individual item is missing within the respective domain. The total score is considered missing if any of the individual item is missing from a giving assessment.

The PUL and DMD Upper Limb PROM total scores will be summarized and analyzed separately using the ANCOVA after MI based on both mITT and ITT populations. The ANCOVA model will include baseline concomitant corticosteroid type (deflazacort, prednisone/prednisolone), baseline 6WMD category (<300 meters, 300 to <350 meters, 350 to <400 meters, ≥400 meters), and treatment as factors, and respective baseline scores as a covariate. The baseline time to stand from supine (<5 seconds, ≥5 seconds) will be included in the testing model in the ITT analysis.

The frequency of losing each PROM item will also be tabulated by treatment group for mITT and ITT populations.

In addition, the PUL total and domain subscores will also be summarized by age group (7 to <8 years old, 8 to <13 years old, 13 to <22 years old, and ≥ 22 years old) using descriptive statistics within each treatment group for mITT and ITT populations. The last assessment during the specific age group will be used for a given subject in this summary.

The PUL total and domain subscores will also be summarized and analyzed for subjects with the following subgroups for ITT population:

- Baseline 6MWD <300 meters
- Baseline 6MWD ≥ 300 meters and time to rise from supine <5 seconds at baseline, or baseline 6MWD ≥ 300 meters, time to rise from supine ≥ 5 seconds at baseline, and younger than 7 or older than 16 years old

